**Table 1. Data Collection Timeline**

Aim s	Data/Variables	Recruitment	T 1	Pre- &post-training	T 2	T 3	Post T3
1,2,3	Consent & sample characteristics	X					
1	Acceptability of OPTIMAL	X					
2	Feasibility of OPTIMAL	X	X	X	X	X	X
	Fidelity of OPTIMAL		X	X	X	X	
	Usefulness of OPTIMAL						X
3	Resident mealtime difficulties, eating performance, intake success rate, BMI		X		X	X	

**Sample Characteristics (Aim 1, 2, 3).** Resident characteristics include age, gender, race, ethnicity, education, dementia stage. Staff and families characteristics include age, gender, race, ethnicity, education, job title (staff only), and length of caregiving.

### **Feasibility, Fidelity, and Usefulness Data (Aim 2)**

**Feasibility of OPTIMAL.** Descriptive data on identification, recruitment, consent, and retention of staff, resident, and family participants will be gathered to assess intervention feasibility (see Appendix 5). In addition to the number of participants screened and eligible for the study, the recruiter will track reasons for those unwilling to participate in the study, and whether that is specifically related to video recording and/or OPTIMAL intervention. We will record the number of participants deemed not eligible and reasons for ineligibility as a basis for planning future trials of OPTIMAL. The length of time it takes to obtain assents/consents from residents, staff, families, and LARs, as well as the number of families and LARs who don't mail back their written consent within expected time period (i.e., 2 weeks after they receive blank consent forms by mail) will be tracked. Families/LARs will be contacted to determine barriers to return of consents and how processes could be changed to facilitate timely return of consent. We will track the number of residents and staff requiring rescheduling of video recording sessions and the reasons for rescheduling. We will track the number of resident and staff participants who withdraw at various time points (e.g., before, during, and after T1, T2, and T3), and those who withdraw will be contacted to determine reasons for withdrawal and how process could be changed to facilitate retention.

**Fidelity of OPTIMAL.** We will assess three aspects of fidelity: 1) delivery of treatment, tracking staff attendance at the group or individual training sessions using a checklist, 2) receipt of treatment, indicated by a total test score of  $\geq 75\%$  on the staff PCMC-related knowledge & self-efficacy test post-training with or without booster sessions (we will track the number of group or individual booster sessions offered in each NH), and 3) enactment of treatment skills, including quality of staff engagement assessed by the 19-item Mealtime Engagement Scale developed

by the PI with evidence of reliability and validity (each item is scored on 0-3, total score range: 0-57, higher score = higher quality of engagement).

**Usefulness of OPTIMAL.** Staff perceived usefulness of the OPTIMAL intervention (OPTIMAL group) or OPTIMAL training session (education control group) will be assessed using semi-structured focus group interviews. Open-ended questions focus on experiences in delivering OPTIMAL care, use of PCMC-related strategies, strategies that do (not) work, and suggestions of refinement for OPTIMAL (see Appendix 7).

### **Resident outcomes (Aim 3)**

**Resident mealtime difficulties.** We will code videos using CUED that has codes for resident mealtime difficulties grouped into three types: 1) chewing and swallowing difficulties represented by 4 behaviors (e.g., holds food in mouth), 2) functional impairment represented by 5 behaviors (e.g., difficulty using utensil), and 3) resistiveness to care represented by 6 behaviors (e.g., doesn't open mouth). Coded data will be used to calculate the number of resident mealtime difficulties by type in each videotaped meal.

**Resident eating performance.** We will use the 9-item Level of Eating Independence scale (see appendix 8) to assess the ability of independence with eating and drinking activities during cycles of verbal prompts. Each item is scored from 1 (total dependence) to 4 (total independence), with total score ranging from 9 to 36 (higher score = more independence). The inter-rater reliability was 0.96.

**Resident intake success rate.** We will code videos using CUED to track whether the resident or staff initiates/completes each intake attempt, and whether there is a subsequent intake after each attempt. We will calculate resident intake success rate through dividing the number of intake attempts initiated/completed by the resident with subsequent intake by the total number of intake attempts coded during one meal.

**Resident Body Mass Index (BMI).** We will assess body weight in the early morning before breakfast with each individual resident dressing casual indoor clothes without shoes using the same digital body scale throughout the study. We will assess body weight twice in one early morning of each time point and calculate the average of the two assessments for BMI.

**Behavioral Coding Procedures for Videos.** All videos will be computer archived and coded second-by-second by trained coders using Noldus Observer® 14.0 following a standard CUED coding manual established by our team. Detailed training and coding procedures are described in PHS HSCTI, 4.4 Statistical Design and Power. Coded data on resident mealtime difficulties and intake process will be exported from Noldus Observer® to excel worksheets, and then imported to SAS 9.4 for us to calculate the number of mealtime difficulties, and intake success rate.

### **Statistical Analysis Plan.**

**Develop, evaluate, and refine OPTIMAL intervention protocol and training materials (Aim 1).** We developed OPTIMAL through systematic integration of four PCMC principles, our prior work on multilevel facilitators and barriers to *engaging residents in eating*, and our systematic review of mealtime difficulties and targeted behavioral strategies. We integrated evidence from literature and our prior work to develop the intervention protocol and training materials, addressing resident mealtime difficulties, targeted PCMC strategies, and establishment of individualized PCMC plans. We conducted focus group interviews of staff participants on the acceptability and appropriateness of the intervention protocol and training materials before pilot testing. Based on

staff overall comments, the OPTIMAL components were highly evaluated as timely and fit to the needs of care practice. Data obtained were used to refine the intervention protocol and training materials before pilot testing.

**Determine feasibility, fidelity, and usefulness of OPTIMAL (Aim 2).** We described feasibility data on participant identification, recruitment, consent and retention, including the number of and reasons for participants' ineligibility, unwillingness to participate, not consenting/assenting, not returning written consent within expected time period, and attrition/withdrawal. We used this information to refine study procedures for a future larger trial to facilitate recruitment and retention. We described treatment fidelity, including staff attendance at training sessions and staff PCMC-related knowledge scores pre- and post-training. Audio-recorded focus group interviews from staff (usefulness) were transcribed and coded. We extracted codes using open coding (using staff's own words) to address the usefulness and areas of refinement of OPTIMAL.

**Describe resident outcomes (Aim 3).** We described distributions of resident eating performance, mealtime challenging behaviors including resistive behaviors and functional impairments, intake success rate, and BMI using appropriate descriptive statistics (mean, median, mode, range, variance, SD, percentile and quartile ranks, n, %) over time. These data were used to inform estimates of effect sizes for sample size calculation in a future trial.

**Expected Outcomes and Impact for Future Trials.** *Using mixed methods, qualitative and quantitative data will be collected and analyzed to refine OPTIMAL intervention protocol, training materials, and study procedures, and to understand its feasibility, fidelity, and usefulness. Data obtained from this pilot trial will provide five critical pieces of information for a future larger efficacy trial. They are:* 1) refined OPTIMAL intervention protocol and training materials with preliminary evidence of feasibility, fidelity, and usefulness; 2) refined study procedures for recruitment, retention, data collection, and recording and behavioral coding of videos; 3) evidence of feasibility for a two-group parallel cluster RCT design with three repeated measures (baseline, 6- & 12-weeks post baseline); 4) effect size estimates of resident outcomes for sample size calculation; and 5) videotaped observations collected in this study to be used in future staff training sessions to illustrate OPTIMAL care skills.

**Limitations.** As a pilot RCT, a small sample of staff and residents from 4 NHs will be enrolled. This is a logical first step to develop and test a new behavioral intervention, prior to a large-scale efficacy trial.

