### Objectives

This study developed and refined OPTIMAL, and evaluated its feasibility, fidelity, and usefulness. The specific aims are:

- 1. Develop, evaluate, and refine OPTIMAL intervention protocol and training materials.** We will integrate evidence from literature and our prior work to develop the intervention protocol and training materials, addressing resident mealtime difficulties, targeted PCMC strategies, and establishment of individualized PCMC plans. We will conduct separate focus group interviews of staff and family participants on the acceptability and appropriateness of the intervention protocol and training materials before pilot testing. Data obtained will be used to refine the intervention protocol and training materials before pilot testing.
- 2. Determine feasibility, fidelity, and usefulness of OPTIMAL.** Feasibility on participant identification, recruitment, consent, and retention will be evaluated descriptively. Fidelity will be assessed on a) delivery of treatment (staff attendance to training sessions), b) receipt of treatment (staff knowledge and self-efficacy post-training), and c) enactment of treatment skills (quality of staff engagement). We will conduct focus group interviews of staff to assess the usefulness of OPTIMAL after T3.
- 3. Describe resident outcomes (Exploratory).** We will measure and describe resident mealtime difficulties, eating performance, intake success rate, and body mass index using descriptive statistics over time for two treatment groups. Data obtained will inform estimates of effect sizes for a future larger-scale trial.

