## Design

We used mixed methods (i.e., focus groups, a pilot single-group repeated measures) to refine and test OPTIMAL. We collected repeated measures at 3 time points: baseline (T1), immediately post intervention (6 weeks post baseline, T2), and 6-week post intervention (12 weeks post baseline, T3). At each time point, we assessed quality of staff engagement and resident outcomes including eating performance and BMI through collection and coding of videotaped observations of dyadic mealtime interaction (videos; Aim 2&3) over 6 meals in 2 consecutive days (2 breakfasts, 2 lunches, 2 dinners) for each staff-resident dyad. We used Cue Utilization and Engagement in Dementia (CUED) mealtime video coding scheme, an innovative, feasible, and reliable tool that our team has developed and validated, and assessed resident mealtime challenging behaviors including resistive behaviors and functional impairments and intake success rate using videos collected in this study.

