Residents are eligible if they: 1) are  $\geq 55$  years, 2) diagnosed as having ADRD based on medical records, 3) identified by NH staff as requiring mealtime assistance, and 4) having a legally authorized representative (LAR) providing informed written consent. Whether the resident needs mealtime assistance is based on medical record review as well as proxy report from the NH staff who has recently cared for the resident at mealtimes using the “feeding” item of the Katz ADL Index. Specifically, residents who need varied levels of assistance with feeding (limited, extensive, total assistance) are eligible, and those who get food from plate into mouth without help are excluded regardless of who prepares food. Residents will be excluded if they: 1) have a documented diagnosis of Parkinson’s disease, traumatic brain injury, or swallowing disorder, 2) do not eat orally (e.g., parenteral/IV feedings, use of feeding tubes), 3) unable to hear or see staff even with glasses and/or hearing aids (e.g., uncorrected visual or hearing impairment), or 4) stay in the NH study site for less than 12 weeks at the time of recruitment/consent/assent (e.g., terminally ill receiving hospice services, and/or receiving post-hospital skilled rehabilitation) that may not allow enough time for obtaining consent/assent, and scheduling days for video recording sessions across three time points (baseline, and 6- and 12-weeks post baseline).

**Recruitment and Consent (Aim 2 and 3).** To enroll staff and families, we will adapt a standard consent protocol for NH dementia mealtime research developed based on our prior study. To enroll residents, we will use a consent& assent protocol for research involving NH residents with dementia and their legally authorized representatives (LARs). Briefly, proxy informed consent will be obtained from the eligible resident’s LAR, and assent from the resident afterwards. Detailed plan is described in the [PHS HSCTI, 2.5 Recruitment and Retention Plan](#).

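### Aim 3 summarises resident outcomes visit by visit, without within-resident change or a link to attrition, so outcome-related loss can shift the T2 and T3 means that inform the future effect size

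*Combined protocol and SAP*

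**What the plan says.** The Design section describes "a pilot single-group repeated measures", with assessments at "baseline (T1), immediately post intervention (6 weeks post baseline, T2), and 6-week post intervention (12 weeks post baseline, T3").

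For Aim 3, the Statistical Analysis Plan describes the resident outcomes "using appropriate descriptive statistics (mean, median, mode, range, variance, SD, percentile and quartile ranks, n, %) over time". These are summaries of each visit's distribution; change within a resident is not among them. On their use, the plan says: "These data were used to inform estimates of effect sizes for sample size calculation in a future trial".

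Attrition is handled elsewhere. Under Feasibility of OPTIMAL: "We will track the number of resident and staff participants who withdraw at various time points", with those who withdraw contacted for their reasons. The Aim 2 paragraph of the Statistical Analysis Plan then reports numbers and reasons for several kinds of non-participation, ending with "not returning written consent within expected time period, and attrition/withdrawal", and uses them to refine procedures. Nothing ties them to the Aim 3 outcomes.

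The eligibility criteria exclude stays under 12 weeks, giving hospice care and post-hospital rehabilitation as examples, and residents who "do not eat orally (e.g., parenteral/IV feedings, use of feeding tubes"). These are conditions at entry.

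The documents do not describe one design throughout. Objectives, aim 3, refers to describing outcomes "using descriptive statistics over time for two treatment groups"; Usefulness of OPTIMAL mentions an education control group; Limitations calls the study a pilot RCT.

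**The concern.** The residents have ADRD and need help with eating, and the Significance section itself links malnutrition to morbidity and mortality. Death, transfer, a move to hospice or an end to oral eating can all occur after T1 despite the entry exclusions. A resident lost this way counts in the T1 distribution but cannot contribute later. Loss can also differ by outcome: a resident who no longer eats by mouth provides no meal to code but can still be weighed, so BMI and the meal outcomes may rest on different residents.

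If those lost were worse at T1, the later means look better through composition alone. In a single group there is no comparator to reveal this. At stake are the effect-size inputs to the next trial, which Expected Outcomes and Impact for Future Trials lists among the pilot's five products. An optimistic input leads to a trial that is too small.

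**Working it through.** **Inputs.** The documents give three visits, marginal summaries and the use for effect sizes. They give no number of residents, expected attrition, SD or effect size, so there is no figure of the plan's own to reproduce. Attrition, gap and SD below are assumptions.

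**Step 1: size of the composition shift.** Let *p* be the fraction lost by a visit, and *S* and *L* the T1 means of stayers and leavers, scored so that higher is better.

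- T1 mean, all residents: (1 − p)S + pL = S − p(S − L).
- Later mean if no one changes: S.
- Apparent change: p × (S − L).

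In baseline SDs:

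| Fraction lost | Gap 0 | Gap 0.5 SD | Gap 1.0 SD |
|---|---|---|---|
| 0.10 | 0 | 0.05 | 0.10 |
| 0.20 | 0 | 0.10 | 0.20 |
| 0.30 | 0 | 0.15 | 0.30 |

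On the 9 to 36 eating-independence scale, 0.30 SD is 0.30 × 5 = 1.5 points for an assumed SD of 5, and 0.30 × 7 = 2.1 points for an SD of 7. If leavers were better at T1, the sign reverses.

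**Step 2: a second route.** Suppose the frailest fraction *d* is lost, and frailty correlates *rho* with the outcome. The shift is rho × φ(z_d)/(1 − d), where φ is the normal density and z_d the normal quantile at *d*. With rho 0.5 it is 0.05, 0.10, 0.17 and 0.25 SD at 5%, 10%, 20% and 30% loss. With rho 0 it is zero throughout. With rho 1 and 30% loss it reaches 0.50 SD, an extreme in which the outcome alone decides who leaves. The two routes agree: at 20% loss and rho 0.5 the implied gap is 0.175/0.20 = 0.875 SD.

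**Step 3: what pairing does.** A simulation of 400,000 residents, with zero mean change overall and rho 0.5, compared the later available mean minus the T1 mean of all residents with within-resident change in those retained.

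| Loss | Visit means, change unrelated to frailty | Paired | Visit means, frail decline faster | Paired |
|---|---|---|---|---|
| 10% | +0.10 | 0.00 | +0.14 | +0.04 |
| 20% | +0.18 | 0.00 | +0.25 | +0.07 |
| 30% | +0.25 | 0.00 | +0.35 | +0.10 |

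Faster decline was set at an assumed 0.2 SD of change per SD of frailty. Pairing removes the composition shift, but not all selection bias.

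**Step 4: possible effect on the next trial.** This assumes the pilot shift is taken as the between-group effect, with individual randomisation, no cluster inflation, two-sided alpha 0.05 and 80% power. With a true effect of 0.30 SD, 175 per arm are needed. Adding 0.175 SD (20% loss, rho 0.5) gives 0.475 SD and 70 per arm, with actual power 43%. Adding 0.097 SD (10% loss) gives about 0.40 SD and 100 per arm, with 56% power.

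**The case against.** A reader might infer that the plan has chosen to analyse whoever remains, and that the pilot will therefore show improvement. The documents support neither. They do not state which residents enter the T2 and T3 summaries, and improvement requires loss related to the outcome, which they do not report. Withdrawal by a representative or loss on the staff side need not be related to frailty.

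The plan has real safeguards. The 12-week-stay exclusion is meant to leave time for all three recording sessions. Withdrawals are tracked by time point with reasons, and *n* is among the listed statistics, so shrinking numbers would be visible. That stands. But the exclusion acts at recruitment only, and counts do not show whether those lost were worse at T1.

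It is also fair that Aim 3 is labelled exploratory and has no hypothesis test, so no efficacy conclusion is at risk. The data only inform the effect sizes, by a route the plan does not spell out. The planned next trial is a two-group cluster RCT, and change in a single group does not estimate its between-group effect even with complete follow-up. Better handling of attrition does not cure that.

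Finally, the protocol refers to PHS HSCTI sections and appendices that are not in these documents; a rule there cannot be excluded.

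**Conclusion.** The point holds in conditional form. As written, Aim 3 relies on marginal summaries at each visit, without within-resident change or a link to attrition, and lets them inform future effect sizes. Outcome-related loss can then shift the T2 and T3 means toward improvement with no resident changing. The size is the fraction lost times the T1 gap: zero if loss is unrelated to the outcome, and 0.30 SD at an assumed 30% loss and 1.0 SD gap. Attrition, gap and SD are all assumptions, so neither the direction nor the size in this pilot can be read from the documents.

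The stronger conclusion, that a spurious benefit passes straight into the next sample size, is not supported: the plan gives no formula, and the figures of 70 and 100 per arm only illustrate what could follow. What remains is a better method available at little cost.

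**What to change.** In the Aim 3 analysis:

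1. Keep the all-available summaries at T1, T2 and T3, with *n* for each outcome and visit.
2. Beside them, report within-resident change T1-T2 and T1-T3 with its SD, using every resident observed at both visits of the pair. Requiring all three visits would discard usable T1-T2 pairs.
3. Tabulate T1 values of residents lost before T2 or T3 against those retained, by reason, with deaths shown separately.
4. Base the change estimates that inform the future effect size on these pairs. State that they apply to residents who remain, and that some selection bias can persist if frailer residents also decline faster.
5. Do not limit BMI to residents still contributing meals. That would drop those who stopped eating by mouth and add selection.

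Reconcile the single-group wording in Design with the two-group, education-control and pilot-RCT wording in Objectives, Usefulness of OPTIMAL and Limitations. If there are two groups, give the same summaries by group.

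The cost is two extra descriptive tables from data the protocol already collects, and a smaller *n* for the paired summaries.

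### On the single-group design, the pilot's changes over time do not estimate the between-arm effect size that the plan offers for sizing a future two-group cluster trial

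*Combined protocol and SAP*

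**What the plan says.** The Design section describes the quantitative part of the study, in the past tense, as "a pilot single-group repeated measures", with measurements at baseline, 6 weeks and 12 weeks: "We collected repeated measures at 3 time points: baseline (T1), immediately post intervention (6 weeks post baseline, T2", followed by T3.

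Under Aim 3, the Statistical Analysis Plan summarises the resident outcomes with descriptive statistics ("mean, median, mode, range, variance, SD, percentile and quartile ranks, n, %) over time"). It names no comparator, contrast, model or interval. Its next sentence gives the use of the results: "These data were used to inform estimates of effect sizes for sample size calculation in a future trial".

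The paragraph on expected outcomes and impact for future trials lists five products for a later efficacy trial. The third is "evidence of feasibility for a two-group parallel cluster RCT design with three repeated measures". The fourth is "effect size estimates of resident outcomes for sample size calculation". Aim 3 in the Objectives states the same effect-size purpose.

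Other places do not fit a single-group study. Aim 3 in the Objectives speaks of describing outcomes "using descriptive statistics over time for two treatment groups". The paragraph on usefulness refers to staff who received the "OPTIMAL training session (education control group"). The Limitations paragraph calls the study a pilot RCT in 4 nursing homes.

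**The concern.** A parallel two-arm trial is sized on the change under the intervention minus the change under the comparator. A single-group pilot observes only the first of these. Over 6 to 12 weeks, residents with dementia may change for reasons unrelated to OPTIMAL: the disease progresses, conditions in the home vary over time, and residents and staff become used to the camera. All of this is included in the T1-to-T2 and T1-to-T3 changes. More residents, better SDs or confidence intervals would not remove it, because the quantity being estimated is a different one.

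What is at stake is the planning of the later trial. If its target difference were taken from these changes, it could be seriously under-powered or much larger than needed, and nothing in the pilot data would show which. No document explains how a within-group change becomes a between-arm difference, or names a source for the change expected in control residents.

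**Working it through.** **No planned figure to reproduce.** The documents give no sample size, effect size, SD, alpha, power, intraclass correlation or cluster size. Every numerical input below is an assumption, chosen to show scale.

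**Step 1: the two quantities.** Let δ be the true between-arm effect and τ the change the same residents would have shown without the intervention, both in between-resident SD units and signed so that positive is benefit.

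- Single-group change: C = δ + τ
- Quantity needed to size a two-arm trial: δ = C − τ

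They are equal only if τ = 0. A single group carries no information on τ.

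**Step 2: sample size.** Assume a two-sided 5% level, 80% power, 1:1 allocation and SD = 1. The normal approximation per arm is

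n = 2(1.960 + 0.842)² / d² = 15.70 / d².

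The two-sample t-test adds one or two per arm.

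| Effect used for sizing | 15.70 / d² | t-test, per arm |
|---|---|---|
| 0.5 (true δ, τ = 0) | 62.8 | 64 |
| 0.7 (τ = +0.2) | 32.0 | 34 |
| 0.3 (τ = −0.2) | 174.4 | 176 |

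**Step 3: consequence when δ = 0.5.**

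- *Favourable drift, τ = +0.2.* The pilot shows 0.7 and the trial is sized at 34 per arm. The noncentrality parameter is 0.5 × √(34/2) = 2.06, and power is about 53% instead of 80%.
- *Unfavourable drift, τ = −0.2.* The pilot shows 0.3 and the trial is sized at 176 per arm, which is 176/64 = 2.75 times the number needed.

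**Step 4: sensitivity to the assumed drift.** Suppose instead that the pilot shows 0.5 SD, the trial is sized at 64 per arm, and control residents would themselves improve by 0.1, 0.2 or 0.3 SD. The true difference is then 0.4, 0.3 or 0.2 SD, and power is about 61%, 39% or 20%.

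**Step 5: clustering.** The sizes above come before cluster inflation. The factor 1 + (m − 1) × ICC, for m residents per home, multiplies each of them alike. It raises the totals but leaves the ratios in Step 3 unchanged.

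**Scale.** All steps use the between-resident SD. A change divided by the SD of change is on another scale, d / √(2(1 − ρ)), where ρ is the within-resident correlation. It matches the between-resident scale only at ρ = 0.5, so the two are not mixed here. The documents do not say which scale their effect sizes would use.

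**The case against.** **The documents do not agree that there is one group.** This objection stands in part. The Objectives, the usefulness paragraph and the Limitations keep two-group, control-group and RCT wording. If two groups were in fact run, a between-group difference could be described, so the point is conditional on the Design section. The conflict does not rescue the plan, however, because the Aim 3 analysis contains no between-group contrast on either reading.

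**The wording is softer than a commitment.** This also stands in part. The Objectives and the analysis plan say only that the data inform effect sizes, and SDs can properly feed a standardised effect size. A reader might infer that the sponsor has adopted the mean T1-to-T2 or T1-to-T3 change as the future target difference. The documents do not say so, and nowhere define the effect size. Still, the list of products promises "effect size estimates of resident outcomes for sample size calculation" outright, and without a control group the data offer no route to a between-arm effect.

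**The future design is inferred.** The plan promises evidence that a two-group cluster trial is feasible, and does not state in so many words that this is the trial to be sized. It is, however, the only future design named. A reader might go further and take the education control as that trial's comparator, so that the pilot change would also include a shared training effect. The documents do not support this: they mention that group only as staff in the present study.

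**This is an exploratory aim in a pilot.** That is true. No feasibility, fidelity or usefulness result changes and no hypothesis test is affected. Any harm depends on how a later protocol uses the figures.

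**Conclusion.** The point holds on the design in the Design section and the analysis in the Statistical Analysis Plan. The changes over time do not estimate the between-arm difference that a two-group cluster trial needs, so the effect sizes offered for its sample size are a product this design does not deliver.

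The size of the error cannot be determined from the documents. On the assumed true effect of 0.5 SD with drift of 0.2 SD either way, planning would land at 34 or 176 per arm instead of 64, with true power of about 53% in the first case. The direction is unknown: decline in untreated residents would make the pilot understate the effect, and improvement would make it overstate the effect.

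A reader might infer that the pilot's Aim 3 data are of no use for planning. That goes too far. The data can still give outcome variability, within-resident correlation, retention and completeness of measurement. A reader might also infer that a favourable outcome or time point will be picked out for the later calculation. Nothing in the documents suggests this.

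**What to change.** 1. Reconcile the statements on design: the single group in the Design section against the two treatment groups in the Objectives, the education control group in the usefulness paragraph, and the pilot RCT in the Limitations.
2. If the study is single-group, reword the effect-size statements in Aim 3 of the Objectives, in the Aim 3 analysis, and in the list of products for future trials. Say that the pilot provides estimates of outcome variability, within-resident correlation, retention and measurement completeness.
3. State that the within-group changes are descriptive and will not serve as the target between-group difference, which must be justified independently of the observed changes.

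If reconciliation shows that two groups were run, the Aim 3 analysis should instead say what between-group description is given.

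The cost is wording in a few places and the loss of one advertised product. No data collection changes, and the feasibility, fidelity and usefulness aims are untouched. The analysis plan is written in the past tense, so the fix does not depend on choosing anything before the pilot results were tabulated.
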